9.3.3. Exposure

Exposure definitions will use the following variables:

- **VKA** will be defined as B01AA ATC code;
- **DOAC** will be defined as B01AF01 ATC code for rivaroxaban and B01AE07 ATC code for dabigatran;
- **DOAC high dosage** will be defined using CIP codes for rivaroxaban 20mg and dabigatran 150mg;
- **DOAC low dosage** will be defined using CIP codes for rivaroxaban 15mg and dabigatran 110mg;
- **Treatment group** will be defined by the first anticoagulant dispensation during the inclusion period, i.e. rivaroxaban high or low dosage, dabigatran high or low dosage, or VKA;
- **Index date** will be defined as the date of the first dispensation of the anticoagulant in the treatment group;
- **Duration of a drug dispensation** will be defined as the number of daily doses for DOAC and 30 days for VKA;
- **Drug (DOAC or VKA) exposure** will be defined as the period starting at the index date and ending at the date of the last drug dispensation plus the duration of the last drug dispensation for subject with a drug discontinuation (defined below) or at the date of drug switch (defined below), or at the end of follow-up, whichever is the earliest;
- **Drug (DOAC or VKA) discontinuation** will be defined with a grace period of 60 days for the main analysis and 30 days for a sensitive analysis after the last dispensation plus the duration of the last drug dispensation;
- **Drug (DOAC or VKA) switch** defined as a dispensation of another anticoagulant, including heparin and LMWH dispensation (B01AB ATC code), for subject with a drug discontinuation;
- **Post drug (DOAC or VKA) exposure** will be defined as the period starting at date of the end of drug exposure (see above) and ending at the date a new prescription of an anticoagulant or at the end of follow-up, whichever is the earliest;
- **DOAC compliance** will be estimated using Medication Possession Ratio (MPR) during drug exposure defined by the number of defined daily doses dispensed, divided by the number of days of drug exposure for DOAC. Considering the variable dosage of VKA between subjects and over time in individual subjects, no defined daily dose can be defined, and therefore no MPR for VKA exposure.
- During a hospitalisation, drugs are provided by the hospital, and this time will be taken into account for calculation of drug exposure and drug discontinuation.

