9.5. STUDY SIZE

The Bordeaux Pharmacoépi (BPE) has performed a previous VKA study in the EGB database, a 1/97 permanent random sample of the SNIIRAM, using similar definitions used in this protocol (Blin 2015). Between 2007 and 2011, the numbers of subjects who initiated a VKA for SPAF were 2 197 for the specific NVAF population and 3 345 for the sensitive NVAF population, which represent about 50 000 and 75 000 subjects respectively in the SNIIRAM each year, and 100 000 and 150 000 respectively for a two-year inclusion period.

Among them, the number of subjects treated with rivaroxaban, dabigatran, and VKA, as well as the number of subjects who can be matched for each comparison (rivaroxaban versus VKA, rivaroxaban versus dabigatran) will be a result of the study. Anyway, it should be clearly higher than the 7 131 and 7 133 subjects randomized in the rivaroxaban and VKA arms of the ROCKET AF trial (Patel 2011).

In the previous VKA study cited above (Blin 2015), the outcome incidence rate during VKA exposure was estimated in the specific NVAF population (with similar results for the sensitive NVAF population):

- Stroke and systemic arterial embolism: 1.6 per 100 person-years (PY), 95%CI [1.1-2.1],
- ACS: 1.6 per 100 PY, 95%CI [1.0-2.1],
- CRB: 2.6 per 100 PY, 95%CI [1.9-3.3], with 0.5 [0.3-0.9] cerebral bleeding hospitalisation, 0.8 [0.4-1.1] digestive bleeding hospitalisation, and 1.3 [0.9-1.8] other bleeding hospitalisation,
- Death: 3.5 per 100 PY, 95%CI [2.7-4.3].

Within the ranges of incidence rates of ROCKET AF trial outcomes, the following table shows the minimum hazard ratio that can be identified with a 95% confidence interval excluding 1, for the study group compared to a reference group, according to the incidence of an outcome in the reference group and the sample size for each group for analysis of matched subjects (1:1).

Minimum hazard ratio (< 1 and > 1) with a 95% confidence interval excluding 1, for the study group compared to a reference group, according to the incidence of an outcome in the reference group, sample size for each group (1:1 matching) and normal distribution

Incidence in the reference group	Hazard ratio	Sample size			
		5 000	10 000	15 000	20 000
0.5%	< 1 / >1	0.24 / 2.19	0.43 / 1.78	0.58 / 1.52	0.65 / 1.42
1.0%	< 1 / >1	0.43 / 1.78	0.58 / 1.52	0.70 / 1.35	0.75 / 1.28
1.5%	< 1 / >1	0.53 / 1.61	0.66 / 1.41	0.75 / 1.28	0.79 / 1.23
2.0%	< 1 / >1	0.59 / 1.52	0.70 / 1.35	0.78 / 1.24	0.82 / 1.20

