9.7.1. Outcomes

Outcomes will be analysed using survival methods for the first occurrence of each outcome:

- Estimation of the one-year and two-year cumulative incidence of each outcome, and according to individual diagnose of each outcome, during drug exposure for rivaroxaban, dabigatran, and VKA, using Kaplan-Meier estimate for death and cumulative incidence function for clinical outcomes, in order to take into account death as a competing risk.
- Estimation of the incidence rate (per 100 PY exposed) of each outcome, and according to individual diagnose of each outcome, during drug exposure or if the risk is not constant over the time, during periods with a constant risk.
- Comparison of the one-year and two-year risk of each outcome during drug exposure, rivaroxaban versus VKA, and rivaroxaban versus dabigatran, using Cox proportional hazard risk model (Cox 1972) for death and Fine and Gray model (Fine 1999) for clinical outcomes, in order to take into account death as a competing risk. Hazard ratio will presented as a point estimate with its 95% confidence interval.
 - Main analysis will compare the incidence of each outcome for matched subjects with time dependant variables adjustment for drug predisposing to bleeding during drug exposure (time dependant variable),
 - Secondary analysis will compare the incidence of each outcome with all subjects, except outliers, with adjustment for hdPS and drug predisposing to bleeding during drug exposure (time dependant variable) for the rivaroxaban versus VKA comparison; and plus low or high DOAC dosage at index date for the rivaroxaban versus dabigatran comparison.
 - Prognostic analysis will be done with all subjects, but outliers, to assess outcome risk factors, including gender, age, CHA₂DS₂-VASc and HAS-BLED scores, low or high dosage at index date for DOAC, drug predisposing to bleeding during drug exposure (time dependant variable) and significant baseline characteristics. The significant baseline characteristics will be identified firstly with univariate analyses, and therefore using a forward stepwise (taking into account the size of the database, the p threshold will be set at 1/1000 for variables selection and at 5% for the stepwise procedure).

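### The detectable-hazard-ratio table in section 9.5 has no person-time term, horizon or stated power, so it is mildly optimistic for the one-year comparison at its implied 90% power; its last two columns do not match their sample-size labels

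*Protocol*

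**What the plan says.** Protocol section 9.5 first quotes outcome rates per 100 person-years during VKA exposure from an earlier VKA study, for example 1.6 for stroke and systemic embolism. It then introduces the table: "Within the ranges of incidence rates of ROCKET AF trial outcomes, the following table shows the minimum hazard ratio", which is set out "according to the incidence of an outcome in the reference group and the sample size for each group for analysis of matched subjects (1:1". The reference trial's stroke and systemic embolism rates are given in section 7 as 1.71% and 2.16% per year. The table has eight incidence rows (0.5% to 5.0%) and four columns (5 000 to 20 000), and its caption names as inputs the incidence and "sample size for each group (1:1 matching) and normal distribution". The criterion is "the minimum hazard ratio that can be identified with a 95% confidence interval excluding 1". No power, time horizon or person-time is given.

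The planned analysis is on-drug. Section 9.7.1 (Outcomes) specifies "Comparison of the one-year and two-year risk of each outcome during drug exposure, rivaroxaban versus VKA, and rivaroxaban versus dabigatran". Section 9.3.3 defines exposure as "ending at the date of the last drug dispensation plus the duration of the last drug dispensation for subject with a drug discontinuation", or at a switch or the end of follow-up if earlier. Section 9.1 sets follow-up at one to two years per subject.

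**The concern.** A rate per person-year becomes an expected number of events only when multiplied by person-years. The table multiplies by subjects. Within a 12-month horizon, mean on-drug time cannot exceed one year, and every stop, switch or death lowers it. The direction of the error for the one-year comparison therefore needs no persistence figure, although its size does.

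The main objective covers two horizons with different amounts of on-drug time, and one table serves both without saying which it describes. This table is the protocol's only statement of what the study can detect. A reader planning around a given matched number, or judging a one-year comparison that shows no difference, would rely on figures whose power, horizon and, in half the columns, sample size are not what they appear to be.

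**Working it through.** **1. Reproducing the table.** Inputs from section 9.5: two-sided 5%, 1:1 groups, normal approximation. Let p1 = incidence, p2 = p1 × HR, p̄ = their mean and d = |p1 − p2|.

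- m = [1.96·√(2p̄(1−p̄)) + z·√(p1(1−p1) + p2(1−p2))]² / d²
- With continuity correction, N = (m/4)·[1 + √(1 + 4/(m·d))]²

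Power is not stated. Of the formulas and powers tried (50% to 95%, with and without correction, and several log-hazard-ratio forms), 90% power with continuity correction (z = 1.2816) fits best. For 1.5% and HR 1.41: p2 = 0.02115, d = 0.00615, m = (0.3693 + 0.2414)²/0.00615² ≈ 9 860, and N ≈ 10 182 against the label 10 000. Solving for HR at exactly 10 000 gives 0.655/1.414 (printed 0.66/1.41). At 0.5% and 5 000 the result is 0.240/2.194 (printed 0.24/2.19). All 32 values in the 5 000 and 10 000 columns agree to rounding, with expected reference events = incidence × head-count.

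**2. The 15 000 and 20 000 columns.** At the labelled N, none of their 32 values reproduces within 0.015. The N that each printed upper value requires is:

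| Incidence | Label | Printed upper HR | N required |
|---|---|---|---|
| 0.5% | 15 000 | 1.52 | 20 222 |
| 1.5% | 15 000 | 1.28 | 20 495 |
| 0.5% | 20 000 | 1.42 | 29 599 |
| 1.5% | 20 000 | 1.23 | 29 611 |

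At N = 20 000 and 30 000 the two columns reproduce, with one exception: 0.89 at 3.0%/20 000, where the formula gives 0.82 at 20 000 and 0.85 at 30 000. At the labelled N, the 1.5% row would be 0.714/1.331 (printed 0.75/1.28) and 0.751/1.284 (printed 0.79/1.23).

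The table shows the mismatch without any formula. Both 1.5% × 5 000 and 0.5% × 15 000 give 75 expected events, yet the cells read 0.53/1.61 and 0.58/1.52. The second pair equals the cell for 1.0% × 10 000, which is 100 events.

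**3. One-year horizon.** The protocol gives no persistence figure, so I assume a constant stopping hazard and one-year persistence s. Mean on-drug time in year 1 is f = (1 − s)/(−ln s). The detectable HR follows from step 1 with incidence × f. Power at the tabulated HR is approximately Φ(3.2415·√f − 1.96), where 3.2415 = 1.96 + 1.2816.

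| s | f (years) | HR at 1.5%/10 000 | Power |
|---|---|---|---|
| full | 1.00 | 0.655/1.414 | 90% |
| 80% | 0.90 | 0.637/1.441 | 87% |
| 70% | 0.84 | 0.626/1.457 | 84% |
| 60% | 0.78 | 0.613/1.476 | 82% |
| 50% | 0.72 | 0.599/1.498 | 79% |

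At 0.5%/10 000, the printed 0.43/1.78 becomes 0.405/1.835 (80%) to 0.347/1.953 (50%).

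**4. Two-year horizon.** With uniform entry over 2013–2014 (assumed) and censoring on 31 December 2015, half the subjects can be followed for 2 years and half for 1 to 2 years, so mean potential follow-up is 0.5 × 2 + 0.5 × 1.5 = 1.75 years. Averaging (1 − s^T)/(−ln s) over these follow-up times T gives mean on-drug times of 1.44, 1.29, 1.15 and 1.00 years for s = 80%, 70%, 60% and 50%. One person-year per subject is then neutral or conservative for the 5 000 and 10 000 columns: at 1.5%/10 000 the result is 0.710/1.337 to 0.655/1.414.

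**The case against.** Four objections deserve weight.

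- **The 90% power is inferred.** The caption reads "Minimum hazard ratio (< 1 and > 1) with a 95% confidence interval excluding 1". Taken literally, this is an observed interval that just excludes 1. At 1.5%/10 000 (150 reference events), solving |ln HR| = 1.96·√(1/150 + 1/(150·HR)) gives 0.786/1.240, closer to 1 than the printed 0.66/1.41. On that criterion the first two columns would be optimistic only below about 0.37 on-drug years per subject, outside the range considered here. This stands: the optimism exists only against the implied 90%, and the document needs to state its power.
- **The row header says only incidence, in per cent.** If a reader enters the on-drug cumulative risk for the chosen horizon, incidence × head-count is correct. The rates quoted immediately before the table make the yearly reading more likely, not certain.
- **Only one of the two horizons is affected.** A reader might infer that precision is overstated for the whole main comparison. Step 4 shows otherwise for the first two columns.
- **The practical effect is small.** Matched numbers come from a national database, and the table fixes no sample size or decision rule.

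Two further inferences are tempting but unsupported. The confidence intervals of the earlier VKA study imply roughly 0.9 to 1.1 on-drug person-years per subject, and a reader might turn this into a one-year persistence near 50%. That requires the study's follow-up time, which the protocol does not give, and it would say nothing about rivaroxaban or dabigatran. A reader might also take the comparison with the reference trial ("Anyway, it should be clearly higher than the 7 131 and 7 133 subjects randomized in the rivaroxaban and VKA arms") as a claim of equal precision. It is a statement about numbers of subjects only and is not an error.

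**Conclusion.** The point holds in limited form. The table lacks a power, a horizon and a person-time term. If its rows are yearly rates and its power is 90%, the 5 000 and 10 000 columns are mildly optimistic for the one-year comparison, by about 0.03 to 0.09 on the upper hazard ratio at 1.5%/10 000 for an assumed persistence of 80% to 50%. The direction follows from the exposure definition; the size rests on the assumed persistence and constant stopping hazard. For two years these columns are neutral or conservative.

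The column error does not depend on persistence. One person-year per subject does not describe the 15 000 and 20 000 columns, which correspond to 1.33 and 1.5 times the labelled number. At 1.5%/15 000 this moves the upper hazard ratio by about 0.05 (1.331 against 1.28), more than 80% persistence does at that size (1.331 to 1.352). The inconsistency between cells with equal expected events is visible in the document itself.

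**What to change.** In section 9.5:

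- State the power and whether each row is a rate per 100 person-years.
- Recompute the table from expected on-drug events = rate per 100 person-years ÷ 100 × N × mean on-drug years, in one block for one year and one for two years, over a stated persistence range such as 50% to 80%.
- Correct the labels or values of the last two columns, and the 0.89 cell at 3.0%/20 000.

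The cost is a recalculated table and a few sentences, with no change to the cohort, the data or the analysis. The downside is that some stated detectable hazard ratios become less favourable, chiefly those for one year and those in the last two columns if the labels are kept.

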9.6. DATA MANAGEMENT

Database extraction criteria will be described in a data extraction plan (DEP) approved prior to initiating extraction. Data extraction will be done by the CNAMTS. The BPE data manager in charge of the project will validate the population extracted by the CNAMTS using the EGB data extraction.

Data transformation, including decision rules, disease definition, exposure definition, outcomes, risk factors, healthcare resources and calculated variables will be detailed in a statistical analysis plan (SAP).

9.7. DATA ANALYSIS

Statistical analysis will be performed using SAS[®] software (SAS Institute, latest current version, North Carolina, USA), and followed the SAP developed and validated by the scientific committee before analysis.

9.7.1. Generalities

The main analysis will be performed with the specific NVAF matched cohorts and a grace period of 30 days for the drug discontinuation definition. A secondary analysis will be performed using a statistical adjustment with all specific NVAF subjects, and a grace period of 30 days for the drug discontinuation definition.

The following sensitive analyses will be performed for matched cohorts, as well as all for statistical adjustment with all subjects:

- With a grace period of 60 days for drug discontinuation definition, in order to take into account the drug supply in real life, or short discontinuation and poor drug adherence;

- With the sensitive NVAF subjects and the two grace periods for drug discontinuation definition;
- With unspecified bleeding classified as haemorrhagic stroke for the specific and the sensitive NVAF cohorts.

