9.3.4. Outcomes

The primary outcomes are:

- **Stroke and systemic embolism (SE)** will be defined as a hospitalisation with one of the two following primary diagnoses:
 - ✓ Ischemic or undefined stroke (Giroud 2015),
 - ✓ Other systemic arterial embolism or surgical procedure for systemic arterial embolism.
- **Major bleeding**, based on International Society on Thrombosis and Haemostasis definition (Schulman 2005) and modified* to take into account the availability of information in the database, will be defined as a hospitalisation with one of the three following primary diagnoses:
 - ✓ Haemorrhagic stroke,
 - ✓ Other critical organ or site bleeding (intrapinal, intraocular, retroperitoneal, intraarticular or pericardial, or intramuscular),
 - ✓ Other bleeding with a transfusion during hospital stay, or resulting in death,

* Causes of death and haemoglobin result are not available to take into account not hospitalized fatal bleeding and bleeding causing a fall in haemoglobin level of 20g/l.
- **Clinically relevant bleeding (CRB)** will be defined as a hospitalisation with one of the five following primary diagnoses:
 - ✓ Haemorrhagic stroke,
 - ✓ Other critical organ or site bleeding (intrapinal, intraocular, retroperitoneal, intraarticular or pericardial, or intramuscular),
 - ✓ Gastro-intestinal bleeding,
 - ✓ Urogenital bleeding,
 - ✓ Other bleeding (ICD-10 codes in annex 1).
- **Death** defined as all-cause death (cause of death not available in the database).
- **Acute coronary syndrome (ACS)** will be defined as a hospitalisation with one of the two following primary diagnoses (Bezin 2015):
 - ✓ Myocardial infarction (MI),
 - ✓ Unstable angina.

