- **Outcomes:** Since deaths are recorded in the database using the national death registry, there is no information bias for this outcome. Death is a competing risk of other clinical outcomes (stroke and SE, ACS, CRB). To take into account this, the model proposed by Fine and Gray will be used to analyse clinical outcomes (Fine 1999). Clinical outcomes will be defined using the ICD-10 discharge primary diagnosis. Miscoding cannot be excluded but should be sparse for the clearly defined events studied. Nevertheless, the PMSI coding is fully independent from the study and there is no reason that a potential miscoding will be different between anticoagulant drugs, excluding an information bias. For strokes classified as undefined because CT scan or NMR were not performed, it was decided to classify undefined stroke with ischemic stroke but some could be cases of haemorrhagic stroke. A sensitivity analysis will be performed by classifying undefined stroke as haemorrhagic stroke.

Counfounding bias

The choice between a VKA and a DOAC could be related to potential confounding. To control this potential bias, the main analysis will use 1:1 matching on high dimensional propensity score (hdPS), which includes main known risk factors (gender, age, AF risk factor score, bleeding risk factor score). Indeed, one of the main limits of this database, as for many administrative databases, is the lack of information for some risk factors (e.g. smoking status, body mass index, biological results, etc.), which may or not be confounders. Without such information, it is not possible to compare the distribution of these risks factors between treatment groups, or to take it into account in the matching.

The propensity score is a statistical technique that attempts to estimate the effect of a treatment, policy, or other intervention by accounting for the covariates that predict receiving the treatment. The propensity score, and more recently hdPS (Schneeweiss 2009, Rassen 2012), were developed to summarise a large set of variables that characterize each subject for status and unmeasured confounders not recorded in a database (i.e. drugs, medical status, hospitalisation, other co-morbidities directly, or indirectly linked with unmeasured confounders). Adjusting for large numbers of covariates ascertained from subject healthcare claims data may improve control of confounding, as these variables may collectively be proxies for unobserved factors.

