O071	Échec d'une tentative d'avortement médical, compliqué d'une hémorragie retardée ou sévère	Failed medical abortion, complicated by delayed or excessive haemorrhage	Hémorragie
O076	Échec d'une tentative d'avortement, autres et sans précision, compliqués d'une hémorragie retardée ou sévère	Other and unspecified failed attempted abortion, complicated by delayed or excessive haemorrhage	Hémorragie
O081	Hémorragie retardée ou sévère consécutive à un avortement, une grossesse extra-utérine et molaire	Delayed or excessive haemorrhage following abortion and ectopic and molar pregnancy	Hémorragie
O208	Autres hémorragies du début de la grossesse	Other haemorrhage in early pregnancy	Hémorragie
O209	Hémorragie du début de la grossesse, sans précision	Haemorrhage in early pregnancy, unspecified	Hémorragie

O441	Placenta praevia avec hémorragie	Placenta praevia with haemorrhage	Hémorragie
O460	Hémorragie précédant l'accouchement avec anomalie de la coagulation	Antepartum haemorrhage with coagulation defect	Hémorragie
O468	Autres hémorragies précédant l'accouchement	Other antepartum haemorrhage	Hémorragie
O469	Hémorragie précédant l'accouchement, sans précision	Antepartum haemorrhage, unspecified	Hémorragie
O670	Hémorragie pendant l'accouchement avec anomalie de la coagulation	Intrapartum haemorrhage with coagulation defect	Hémorragie
O678	Autres hémorragies pendant l'accouchement	Other intrapartum haemorrhage	Hémorragie
O679	Hémorragie pendant l'accouchement, sans précision	Intrapartum haemorrhage, unspecified	Hémorragie
O720	Hémorragie de la délivrance (troisième période)	Third-stage haemorrhage	Hémorragie
O721	Autres hémorragies immédiates du post-partum	Other immediate postpartum haemorrhage	Hémorragie
O722	Hémorragie du post-partum, tardive et secondaire	Delayed and secondary postpartum haemorrhage	Hémorragie
R040	Épistaxis	Epistaxis	Epistaxis
R041	Hémorragie de la gorge	Haemorrhage from throat	Hémorragie
R042	Hémoptysie	Haemoptysis	Hémoptysie
R048	Hémorragie d'autres parties des voies respiratoires	Haemorrhage from other sites in respiratory passages	Hémorragie
R049	Hémorragie des voies respiratoires, sans précision	Haemorrhage from respiratory passages, unspecified	Hémorragie
R31	Hématurie, sans précision	Unspecified haematuria	Hématurie
R58	Hémorragie, non classée ailleurs	Haemorrhage, not elsewhere classified	Hémorragie
S064	Hémorragie épidurale	Epidural haemorrhage	Hémorragie
S065	Hémorragie sous-durale traumatique	Traumatic subdural haemorrhage	Hémorragie

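### Sections 9.7.1 and 9.9 give incompatible rules for the stroke-misclassification sensitivity analysis, and the one listed in 9.7.1 cannot test the ambiguity that 9.9 describes

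*Protocol*

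**What the plan says.** Section 9.3.4 defines the primary outcome stroke and systemic embolism (SE) to include "Ischemic or undefined stroke" as a primary diagnosis. Haemorrhagic stroke sits elsewhere, as an unconditional component of both major bleeding and clinically relevant bleeding (CRB). Bleeding outside the critical sites counts as major only under a further condition: "Other bleeding with a transfusion during hospital stay, or resulting in death".

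Section 9.9, under outcomes, recognises the weak point. For strokes left undefined because no imaging was done, "it was decided to classify undefined stroke with ischemic stroke but some could be cases of haemorrhagic stroke". It then commits to a remedy: "A sensitivity analysis will be performed by classifying undefined stroke as haemorrhagic stroke".

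Section 9.7.1, which lists the sensitivity analyses to be run, does not contain that analysis. Its last item reads: "With unspecified bleeding classified as haemorrhagic stroke for the specific and the sensitive NVAF cohorts". The data analysis part of the abstract carries the same wording.

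**The concern.** The two statements move different events. Undefined stroke is the class that the protocol itself identifies as possibly lying on the wrong side of the line between the primary benefit outcome (stroke/SE) and the primary harm outcome (major bleeding). Unspecified bleeding is already on the bleeding side, so relabelling it says nothing about that line.

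A programmer who works from the list in 9.7.1 would run the version without a rationale, and would run it for matched and adjusted analyses in both the specific and the sensitive cohort. The question raised in 9.9 would then go unanswered. The question is not idle: section 7 reports that the pivotal trial found different intracranial haemorrhage rates on rivaroxaban and warfarin (0.5% against 0.7%), so the haemorrhagic fraction among undefined strokes need not be the same in the two arms.

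**Working it through.** The protocol states no figure to reproduce. The check is to follow each rule through the outcome definitions in 9.3.4.

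| Outcome | Rule in 9.9 (undefined stroke becomes haemorrhagic stroke) | Rule in 9.7.1 and abstract (unspecified bleeding becomes haemorrhagic stroke) |
|---|---|---|
| Stroke/SE | Falls: events leave it | Unchanged |
| Haemorrhagic stroke | Rises | Rises, if the recoded bleeds were not already there |
| Major bleeding | Rises by the same events | Rises by recoded bleeds that had neither transfusion nor death |
| CRB | Rises | Total unchanged: the events were already CRB |
| Composite of stroke/SE, major bleeding and death | Essentially unchanged: events move between components | Rises with major bleeding |

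Only the first column moves anything across the ischaemic/haemorrhagic line.

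**Can the 9.7.1 wording be read as meaning undefined stroke?** The selected bleeding codes in Annex 1 contain no code for a stroke of undefined type. Codes that fit the word unspecified include R58 ("Haemorrhage, not elsewhere classified"), D699 (haemorrhagic condition), K922 (gastrointestinal), N939 (uterine and vaginal) and R049 (respiratory). None of these is a stroke. I629, unspecified non-traumatic intracranial haemorrhage, also fits, but it is already a bleeding code. Annex 1 does not allocate codes to the subclasses of 9.3.4, so the documents do not settle whether the phrase means I629 alone or the wider set. Stroke/SE stays unchanged on either reading.

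**Illustration of size.** The rates come from section 9.5 (earlier VKA study, specific population, per 100 person-years): stroke/SE 1.6, cerebral bleeding 0.5, digestive bleeding 0.8, other bleeding 1.3. Cerebral bleeding stands in for haemorrhagic stroke. The shares *s* and *u* are assumptions; nothing in the protocol supports any value. The sums ignore that only first events count.

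- Rule in 9.9: events moved = *s* × 1.6.
  - *s* = 5%: 0.05 × 1.6 = 0.08. Stroke/SE 1.6 − 0.08 = 1.52; haemorrhagic stroke 0.5 + 0.08 = 0.58.
  - *s* = 30%: 0.30 × 1.6 = 0.48. Stroke/SE 1.12; haemorrhagic stroke 0.98.
- Rule in 9.7.1, unspecified bleeds drawn from other bleeding only: events relabelled = *u* × 1.3.
  - *u* = 10%: 0.13. Haemorrhagic stroke 0.63; stroke/SE 1.60.
  - *u* = 50%: 0.65. Haemorrhagic stroke 1.15; stroke/SE 1.60.
- Rule in 9.7.1, digestive bleeding included: *u* × (0.8 + 1.3) = *u* × 2.1.
  - *u* = 10%: 0.21. Haemorrhagic stroke 0.71.
  - *u* = 50%: 1.05. Haemorrhagic stroke 1.55.
- Rule in 9.7.1, I629 only: no extracranial bleed is relabelled, and the change may be nil.

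These ranges show direction. Their width reflects the chosen shares and the reading of an undefined term.

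**The case against.** The strongest reply is that the protocol does commit to the right analysis. Section 9.9 states it in plain terms with its reason, section 9.6 leaves decision rules for outcomes to the SAP, and section 9.7 has the scientific committee validate the SAP before analysis. Literal execution of the 9.7.1 wording is therefore not certain. This stands, and it limits the point to a contradiction that needs reconciling. It does not remove the contradiction: the protocol fixes two different rules, which is not the same as leaving a detail open.

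A second reply is that two separate analyses may be intended. The text does not exclude this. In that case, however, the analysis promised in 9.9 is missing from the list in 9.7.1, and the listed one lacks both a definition and a rationale.

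A reader might also infer more than the documents support. One inference is that undefined stroke will never be tested; this is true only if 9.7.1 is followed and 9.9 is overlooked. Another is that the study's haemorrhagic-stroke and major-bleeding results are contaminated. The item appears only among the sensitivity analyses, and the main and secondary analyses use the definitions in 9.3.4. Even within the sensitivity run, relabelling of non-cranial bleeds depends on how the undefined term is read.

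**Conclusion.** The point holds as an internal contradiction in current text; the protocol's amendment table is empty, so neither wording is superseded. The rule in 9.7.1 and the abstract is wrong for the purpose given in 9.9, because it cannot change stroke/SE under any reading of the term. The possible counting of non-cranial bleeds as haemorrhagic strokes is a conditional further consequence, limited to that sensitivity run. No primary or secondary estimate is affected.

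The effect cannot be sized from the documents, since the shares of undefined strokes and of unspecified bleeds are not given. The conclusion rests on comparing the sections and not on the illustrative rates. It is worth correcting before the SAP is written, but it is a modest point about one sensitivity analysis.

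**What to change.** In section 9.7.1 and in the abstract, replace unspecified bleeding with undefined stroke, in line with 9.9. Add one clause saying that in this run the events leave stroke/SE and enter haemorrhagic stroke, hence major bleeding and CRB.

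If a separate analysis of unspecified bleeding is really wanted, list it in addition, with its Annex 1 codes and the reason for treating them as haemorrhagic stroke.

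The cost is a two-word change in two places and one clarifying clause. No new data are needed, and no analysis beyond the one that 9.9 already promises.
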